2.7 Statistical Analysis and Sample Size Justification	
The investigator will analyze the study data. The blind will be maintained using blinded medication and matching placebo provided by the sponsor. For the final analysis, the clinical database will not be unblinded until medical/scientific review has been completed, protocol violators have been identified (if appropriate), and data has been declared complete. Data will then be unblinded, data analysis will be completed, and the manuscripts will be prepared for publication.
 
Variables/Time Points of Interest
 
Primary outcome – subjective total sleep time (sTST), according to self-report, assessed at Controlled Week-0, Controlled Week-1, Open month-1, Open month-2, and Open month-3.
 
Secondary outcome – objective total sleep time (oTST), according to Actigraph, assessed at Controlled Week-0, Controlled Week-1, Open month-1, Open month-2, and Open month-3.
 
Statistical Methods
 
For the randomized controlled phase, the primary outcome (change in sTST from Controlled Week-0 to Controlled Week-1) for adjunctive suvorexant versus adjunctive placebo will be assessed using a Mixed-Effect Model Repeated Measure (MMRM), with a significance threshold of $p < 0.05$.

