	
For this 1-week, double-blind, placebo-controlled trial, assuming a two-tailed alpha of .05, a sample of 50 patients (25 patients taking double-blind adjunctive suvorexant, and 25 patients taking adjunctive placebo) would be required to detect an adjunctive suvorexant treatment effect (compared to adjunctive placebo) of 0.70, with a power of approximately .80, as described in greater detail below.
 
For the open extension study, the key efficacy outcome will be change in sTST from Controlled Week-0 to Open Month-3, stratified by acute treatment arm (i.e., blind adjunctive suvorexant followed by open adjunctive suvorexant, and blind adjunctive placebo followed by open adjunctive suvorexant), using a paired Mixed-Effect Model Repeated Measure (MMRM) analysis, with a significance threshold of $p < 0.05$.
 
Additional secondary analyses include evaluation of change in oTST from Controlled Week-0 to Controlled Week-1 for adjunctive suvorexant versus adjunctive placebo, using MMRM with a significance threshold of $p < 0.05$; and change in oTST from Controlled Week-0 to Open Month-3, stratified by acute treatment arm (i.e., blind adjunctive suvorexant followed by open adjunctive suvorexant, and blind adjunctive placebo followed by open adjunctive suvorexant), using a paired MMRM analysis, with a significance threshold of $p < 0.05$.
 
There are no adjustments for dropout, as we expect no more than 5% dropout by the end of week 1.
 
Multiplicity
 
No correction for multiple comparisons will be used.
 
Power/Sample Size:
 
Based on pooled results in Table 1 of Herring, et al.,¹⁴ we expect baseline mean (SD) sTST in minutes of 317 (64). We expect a robust sTST benefit with suvorexant (60 min increase) compared to placebo (15 minute increase) - admittedly this is a more marked suvorexant-placebo difference (60-15 = 45 minutes, which yields an effect size of 0.70) than in Herring et al. Supplemental Table S1,¹⁴ which had a pooled suvorexant-placebo difference of 33-15 = 18 minutes, which yielded a pooled effect size of only 0.28.
 
Thus, for the primary outcome of the randomized controlled phase, based upon a sample size of n=25 patients per group, and a two-tailed alpha of 0.05, this study has 80% power to detect an effect difference in change in sTST for suvorexant versus placebo of 0.70.

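### The 0.70 effect size divides 45 minutes by a baseline SD although the endpoint is a change score, and at 0.70 with 25 per arm power is about 68%, not 80%

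*Combined protocol and SAP*

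**What the plan says.** Under Statistical Methods in Section 2.7, the primary comparison is "change in sTST from Controlled Week-0 to Controlled Week-1", suvorexant against placebo, by MMRM at p < 0.05. No covariates are listed.

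The same section sets the size of the trial as "assuming a two-tailed alpha of .05, a sample of 50 patients", split as "25 patients taking double-blind adjunctive suvorexant, and 25 patients taking adjunctive placebo".

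The Power/Sample Size paragraph takes its spread from a published pair of suvorexant trials: "we expect baseline mean (SD) sTST in minutes of 317 (64"). It then sets the expected benefit as "60-15 = 45 minutes, which yields an effect size of 0.70". For comparison it cites the published result as a "pooled suvorexant-placebo difference of 33-15 = 18 minutes, which yielded a pooled effect size of only 0.28". It concludes that "this study has 80% power to detect an effect difference in change in sTST for suvorexant versus placebo of 0.70".

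The divisor is not written out for either effect size. The paragraph contains no other SD, and the plan gives no correlation between visits and no residual SD.

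**The concern.** A difference in mean change has been standardised by the spread of sTST between patients at a single time point. The spread of change within patients is a different quantity. It depends on how strongly a patient's Week-0 and Week-1 values are correlated, and it can be larger or smaller than the baseline SD. Without that correlation, or an SD of change, the step from 45 minutes to 0.70 is unsupported for the endpoint under test.

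The power figure also needs checking on its own terms, because 80% is what justifies 25 per arm. The plan itself admits that 45 minutes is well above the 18 minutes seen in the published trials. If the result is null, a reader will want to know what difference in minutes the trial was able to detect, and the plan does not say.

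**Working it through.** **Inputs (all from Section 2.7).** Difference 45 min; baseline SD 64 min; n = 25 per arm; two-sided alpha 0.05; stated power 80%. The correlation r is not in the documents and is varied below as an assumption.

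**Step 1: where 0.70 comes from.** 45/64 = 0.703 and 18/64 = 0.281. Both match the plan's 0.70 and 0.28, so the divisor is the baseline SD in each case.

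**Step 2: the plan's own power figure.** With d = 0.70, the normal approximation is Φ(d·√(n/2) − 1.96) = Φ(0.70 × 3.536 − 1.96) = Φ(0.515) = 69.7%. The two-sample t-test (noncentral t, 48 df) gives 67.9%. Using 45/64 unrounded gives 70.1% and 68.3%. The stated 80% is not reproduced.

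- 80% power with 25 per arm needs d of about 0.81 by t-test, which is 0.809 × 64 = 52 min at an SD of 64.
- 80% power at 0.70 needs 33 (normal) or 34 (t) per arm.
- A one-sided 0.05 test gives 79.7% at 0.70, but the plan says two-tailed.
- With 24 completers per arm (about the 5% dropout that the plan expects), power for 45 min at an SD of 64 is about 66% (t).

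**Step 3: the scale of the endpoint.** Assume equal variances at Week-0 and Week-1.

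- Unadjusted change score: SD = 64·√(2(1 − r)).
- Adjusted for baseline: residual SD = 64·√(1 − r²).

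The detectable difference at 80% power is 0.809 × SD. All power figures are by t-test for 45 min with 25 per arm.

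| Assumed r | SD of change | Power, unadjusted | Detectable, unadjusted | Residual SD | Power, adjusted | Detectable, adjusted |
|---|---|---|---|---|---|---|
| 0.3 | 75.7 | 54% | 61 min | 61.1 | 72% | 49 min |
| 0.5 | 64.0 | 68% | 52 min | 55.4 | 80% | 45 min |
| 0.7 | 49.6 | 88% | 40 min | 45.7 | 93% | 37 min |

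Under the equal-variance assumption, the SD of change equals 64 only at r = 0.5. For an unadjusted analysis to have 80% power for 45 min, the SD of change must be about 56 min or less. That means (56/64)² = 0.766 = 2(1 − r), so r is about 0.62 or more.

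**The case against.** The strongest reply has four parts.

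- **The endpoint is named correctly.** A reader might infer that the power claim refers to some other endpoint, or that the whole calculation is on the wrong scale. The documents do not support that. The closing sentence of the power paragraph names the change in sTST, and power at a standardised effect of 0.70 does not depend on any SD. Only the link from 45 minutes to 0.70 lacks support. This part stands.
- **The direction is unknown.** A reader might also infer that using the baseline SD makes the trial underpowered. The documents do not show this. At r = 0.5 the substitution changes nothing, and above 0.5 it is conservative. If the MMRM adjusts for baseline, the residual SD is never above 64 and the baseline SD is conservative throughout. This stands too, but the plan states neither r nor the adjustment.
- **80% can be recovered.** Baseline adjustment with r = 0.5 gives 80.3% for 45 minutes. The arithmetic is right, but it rests on two assumptions that the plan does not make. The plan claims 80% at an effect size of 0.70, and at that value power is about 68%.
- **The practical effect is limited.** A null result is read mainly from its confidence interval, which uses the observed SD, and the correction changes no patient number, endpoint or test. That limits the weight of the point. It does not make the stated power correct.

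**Conclusion.** The point holds, in two parts of different strength.

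The firm part is numerical. The plan's own inputs give about 68% power (t-test), or 70% by normal approximation, where it states 80%. This needs no outside assumption and remains true if 64 is accepted as the right SD.

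The second part is a missing justification. The effect size of 0.70 is scaled by a baseline SD and then applied to a change score, with no SD of change, correlation or covariates given. Over r from 0.3 to 0.7 with equal variances, both of which are assumptions, power for 45 minutes is 54% to 88% unadjusted and 72% to 93% adjusted. The range falls on both sides of 80%, so this part does not show that the trial is too small.

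All figures take 25 per arm from Section 2.7. Section 2.8 counts drug supply for 50 patients per arm; that is a separate discrepancy and is not resolved here.

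**What to change.** Keep 25 per arm and rewrite the Power/Sample Size paragraph, and the matching sentence earlier in Section 2.7, as follows:

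- Replace the 80% statement with about 68% power for 45 minutes at an SD of 64, two-sided 0.05.
- State the SD of change, or the baseline SD with an assumed Week-0/Week-1 correlation, and say what the assumption rests on.
- State whether the MMRM adjusts for baseline sTST, and list any other covariates.
- Give the power for 45 minutes and the difference detectable with 80% power as ranges. Over r from 0.3 to 0.7, the detectable difference is about 40 to 61 minutes unadjusted and 37 to 49 minutes adjusted.
- Say that the 0.28 quoted for the published trials uses the same baseline divisor.

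The documents do not say whether Week-0 and Week-1 data have been collected. If they are available and still blinded, the pooled SD of change can inform the assumption without unblinding. Any treatment effect inflates it slightly: with a true SD of 64 and a 45-minute difference between equal arms, the pooled value is √(64² + 22.5²), or about 68.

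The cost is one recalculation and a less favourable stated figure. No patients are added.

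### The stated 80% power is wrong: 25 patients per arm, an effect size of 0.70 and two-tailed alpha 0.05 give about 68%

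*Combined protocol and SAP*

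**What the plan says.** Section 2.7 makes the power claim twice. Under Statistical Methods it says that "a sample of 50 patients (25 patients taking double-blind adjunctive suvorexant, and 25 patients taking adjunctive placebo) would be required" for an effect size of 0.70; the power is given there in rounded form ("with a power of approximately .80, as described in greater detail below"). Under Power/Sample Size it says, without the word approximately, that "based upon a sample size of n=25 patients per group, and a two-tailed alpha of 0.05, this study has 80% power". The effect size in question is defined on the change itself: "to detect an effect difference in change in sTST for suvorexant versus placebo of 0.70".

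The 0.70 comes from an expected 60-minute gain on suvorexant and 15-minute gain on placebo ("60-15 = 45 minutes, which yields an effect size of 0.70"), divided by an SD of 64 minutes that is introduced as a baseline SD. On attrition, the section says: "There are no adjustments for dropout, as we expect no more than 5% dropout by the end of week 1". It also says that no correction for multiple comparisons will be used, so alpha for the primary test stays at 0.05.

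**The concern.** Sample size, allocation, alpha, sidedness and standardised effect are all stated, so the power follows from them and can be checked. A common rule of thumb (16 divided by the squared effect size, here 16/0.49 = 32.7) already puts the requirement for 80% power at about 33 per arm rather than 25.

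This claim is the only justification given for the size of the primary comparison. If it is wrong, the trial is less sensitive than its readers are told, even under an effect that the plan itself admits is larger than in its cited source (45 minutes against 18, or 0.70 against 0.28). A non-significant result would then count as stronger evidence against the drug than the design supports.

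**Working it through.** **Inputs, all from section 2.7.** n = 25 per arm; two-tailed alpha 0.05; d = 0.70 (unrounded, 45/64 = 0.703); stated power 0.80; dropout of at most 5% with no inflation.

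**Power from the stated inputs.** For two equal arms the noncentrality is d × √(n/2), with 2n − 2 = 48 degrees of freedom.

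- Noncentrality: 0.70 × √12.5 = 2.475. The two-sided critical value of t on 48 df is 2.011.
- Exact power (noncentral t): **67.9%**. At d = 0.703 it is 68.3%.
- Normal approximation: Φ(2.475 − 1.960) = Φ(0.515) = 69.7%. At d = 0.703 it is 70.1%.

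The stated 80% is not reproduced. The gap is about 12 points by the t-test and 10 by the normal approximation, too large for rounding.

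**What would reproduce it.** With one-sided alpha 0.05 the critical value falls to 1.677 and power is 78.7% (t) or 79.7% (normal). That is close to the printed figure, but both sentences say two-tailed. A one-sided calculation is therefore a possible origin, not an established one.

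**Effect of dropout.** Five per cent of 25 is 1.25, leaving about 24 per arm. Noncentrality is 0.70 × √12 = 2.425, and power is 66.1%. This is the plan's upper limit for dropout and costs about 2 points.

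**Effect detectable with 80% power at 25 per arm.** Solving the noncentral t for d gives 0.809. By normal approximation, (1.960 + 0.842) × √(2/25) = 0.792. At SD 64 the exact figure is 0.809 × 64 = 51.8 minutes, against the planned 45.

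**Sample size for 80% at d = 0.70.** By normal approximation, 2 × (1.960 + 0.842)² / 0.49 = 32.04, so 33 per arm. By the exact t-test, 33 per arm gives 79.97%, so 34 is the smallest number that reaches 80%. At d = 0.703 it is 33.

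**Power if the model uses the baseline value.** The plan gives no correlation, so the correlations below are assumptions. They take 64 minutes as the raw SD at both visits. Baseline adjustment divides d = 0.70 by √(1 − r²). An unadjusted change score has SD 64 × √(2(1 − r)), applied to the 45-minute difference.

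| Assumed correlation r | Baseline-adjusted power | Unadjusted change-score power |
|---|---|---|
| 0.3 | 72% | 54% |
| 0.4 | 75% | 60% |
| 0.5 | 80% | 68% |
| 0.6 | 86% | 78% |

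Power crosses 80% at a correlation of about 0.50 with adjustment and about 0.62 without it.

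**The case against.** The strongest defence is that the primary analysis is an MMRM, not a t-test, and that 64 minutes is a baseline SD while the outcome is change. If the model adjusts for baseline and the correlation is about 0.5, 25 per arm does give about 80% for a 45-minute difference. On that view the power of the planned analysis cannot be fixed from the documents, and the miss rate across the table above runs from 14% to 46%.

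Part of this stands. Figures in minutes, and the one-in-three miss rate for a 45-minute effect, hold only if the SD that applies in the analysis is 64. The defence does not rescue the printed claim, though. Section 2.7 names no baseline covariate, no correlation and no SD of change, and its closing sentence applies 0.70 directly to the difference in change. For a claim already standardised on change, a different SD alters the minutes that 0.70 represents, not the power at 0.70. The unstated choice can also work the other way, since an unadjusted change score at a correlation of 0.3 gives 54%.

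Two smaller points are fair. Dropout of 5% is the plan's ceiling, so 66% is the lower end rather than the expected value. Also, section 2.8 plans drug supply for 50 patients per arm. That number would give about 93% power at 0.70, so it does not explain 80% either, and it conflicts with the 25 per arm in section 2.7.

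**Conclusion.** The concern holds. On the plan's stated inputs, power for the primary test is about 68% (70% by normal approximation), not 80%. At the 5% dropout ceiling it is about 66%. With 25 per arm, 80% power belongs to an effect of about 0.81 SD, and 80% at 0.70 needs 34 per arm.

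The 68%, the 0.81 SD and the 34 per arm rest only on the stated alpha, sidedness, arm sizes and standardised effect. The 52-minute equivalent also assumes an SD of 64. Because the error concerns the justification of the primary comparison and appears twice, it must be corrected.

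**What to change.** Correct both sentences in section 2.7 to say that 25 patients per arm give about 68% power for an effect of 0.70 at two-tailed alpha 0.05 (about 66% if dropout reaches 5%), and that 80% power applies to an effect of about 0.81 SD, or 52 minutes at an SD of 64.

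If the sponsor wishes to keep a figure near 80%, section 2.7 should name the baseline-adjusted primary model, state the assumed correlation between baseline and Week-1 sTST with its source, and show the calculation. A correlation of 0.5 would give about 80% with 25 per arm, before any dropout.

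While the section is open, the 25 per arm there and the 50 per arm in section 2.8 should be reconciled, so that the power statement rests on the number actually planned.

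The power correction costs protocol wording only. It needs no change to procedures, endpoint or enrolment target. The price is a less favourable stated power.

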
2.3 Study Design
	
Patients with bipolar disorder (Type I, Type II, or Type Not Otherwise Specified) who are currently euthymic or have current syndromal or subsyndromal depressive (but not hypo/manic) symptoms (i.e. have Young Mania Rating Scale [YMRS]⁷ total score < 12), and with insomnia related to bipolar disorder (307.42), with subjective total sleep time (sTST) < 6 hours on at least 1 night during the prior week, will be randomized to receive either adjunctive double-blind placebo or adjunctive double-blind suvorexant 10 mg at bedtime for 3 nights, which as necessary and tolerated then may be increased to 20 mg at bedtime for 4 nights. In all patients, there will be an attempt to increase Suvorexant/Placebo dose from 10 to 20 mg at bedtime after three nights (although Suvorexant/Placebo dose may remain at 10 mg if the patient prefers to do so, though this is expected to be uncommon). Following the 1-week randomized controlled phase, all patients will receive open suvorexant 10 mg at bedtime for 3 nights, which as necessary and tolerated then may be increased to 20 mg at bedtime for 3 months. All patients (i.e. those in both the active drug and placebo group) will revert back to the 10mg dose at the start of the open treatment phase in order to protect the blind.
 
Inclusion Criteria:
 
 1. Adult outpatients (age 18 years and older) meeting Diagnostic and Statistical Manual of Mental Disorders, Fourth Edition, Text Revision (DSM-IV-TR)⁸ criteria for bipolar I disorder (296.70), bipolar II disorder (296.89), or bipolar disorder not otherwise specified (296.80), with concurrent insomnia related to bipolar disorder (307.42). 2. Currently taking ≥ 1 prescription psychotropic medication (hypnotic agents, anxiolytics, atypical antipsychotics, mood stabilizers, and/or antidepressants) for management of bipolar disorder. 3. Subjective total sleep time (sTST) < 6 hours on ≥ 1 night during the prior week, assessed at baseline visit using the Systematic Treatment Enhancement Program for Bipolar Disorder (STEP-BD) Clinical Monitoring Form (CMF).⁹ 
Exclusion Criteria:
 
 1. Current hypo/manic symptoms, as evidenced by YMRS total score ≥ 12, assessed at baseline visit. 2. Current (past 6 months) alcohol or substance use disorder, as determined by assessment with the Mini-International Neuropsychiatric Interview (MINI)¹⁰ at baseline visit. 3. Current psychosis, as determined by assessment with the MINI at baseline visit.

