2.8 Specific Drug Supply Requirements	
Suvorexant 10 mg tablets, 20mg tablets, and matching placebo will be supplied by Merck.
 
Drug Supply Requirements:
 
Drug Name: Suvorexant 10 mg tablets. Amount: 3 tabs for days 1-3 of 1-week, randomized, controlled treatment phase (a total of 150 tabs for 50 double-blind suvorexant patients), then 3 tabs for days 1-3 of 3-month open treatment phase (a total of 300 tablets for 100 open suvorexant patients). Total 450 Suvorexant 10 mg tablets.
 
Drug Name: Suvorexant 20 mg tablets. Amount: 4 tabs for days 4-7 of 1-week, randomized, controlled treatment phase (a total of 200 tabs for 50 double-blind suvorexant patients), then 87 tabs for days 4-90

	
of 3-month open treatment phase (a total of 8700 tablets for 100 open suvorexant patients).
 
Total 8900 Suvorexant 20 mg tablets.
 
Drug Name: Placebo tablets (to match suvorexant 10mg tablets). Amount: 3 tabs for days 1-3 of 1-week, randomized, controlled phase (a total of 150 tablets for 50 double-blind placebo patients).
 
Total 150 placebo tablets (to match suvorexant 10mg tablets).
 
Drug Name: Placebo tablets (to match suvorexant 20mg tablets). Amount: 4 tabs for days 4-7 of 1-week, randomized, controlled phase (a total of 200 tablets for 50 double-blind placebo patients).
 
Total 200 placebo tablets (to match suvorexant 20mg tablets).
 
Note: At conclusion of the study or upon drug expiration, the Merck GRS will be responsible for issuing a Drug Disposition Letter to the investigator for US based studies.
 
The investigator will be responsible for the destruction of the supplies at the study center pursuant to the ICH/GCP Guidelines, local regulations and the investigator's institutional policies. Clinical supplies will be received by [name] at the study site, handled and stored safely and properly, and kept in a secured location to which only the investigator and designated assistants have access. Clinical supplies will be dispensed in accordance with the protocol. The investigator is responsible for keeping accurate records of the clinical supplies, the amount dispensed to and returned by the patients, and the disposition at the end of the study.

2.9 Adverse Experience Reporting	
Adverse experience reporting will be conducted as outlined by the Model Study Agreement.

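### Section 2.7 plans 50 randomised patients while the drug supply in 2.8 implies 100, and 2.7's 80% power does not follow from its stated inputs

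*Combined protocol and SAP*

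**What the plan says.** Section 2.7 (Statistical Analysis and Sample Size Justification) gives the size of the randomised phase as "a sample of 50 patients (25 patients taking double-blind adjunctive suvorexant, and 25 patients taking adjunctive placebo", and its power paragraph repeats "based upon a sample size of n=25 patients per group". The claim is 80% power at a two-tailed alpha of 0.05 for an effect size of 0.70. That effect size is a 45-minute difference (60 minus 15) divided by 64, and 64 enters as a baseline figure: "we expect baseline mean (SD) sTST in minutes of 317 (64". The primary outcome is "change in sTST from Controlled Week-0 to Controlled Week-1". On attrition, 2.7 says: "There are no adjustments for dropout, as we expect no more than 5% dropout by the end of week 1".

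Section 2.8 (Specific Drug Supply Requirements) counts patients explicitly. The 10 mg suvorexant line is worked out "for 50 double-blind suvorexant patients), then 3 tabs for days 1-3 of 3-month open treatment phase", and its open-phase part is for 100 patients. The 20 mg suvorexant line uses the same 50 and 100, and both placebo lines use 50.

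Section 2.3 (Study Design) links the two phases: "Following the 1-week randomized controlled phase, all patients will receive open suvorexant". It also allows an exception to the move to 20 mg: "although Suvorexant/Placebo dose may remain at 10 mg if the patient prefers to do so".

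**The concern.** Because every randomised patient goes on to open treatment, the open-phase count cannot exceed the randomised count. Section 2.7 therefore allows at most 50 open patients, while 2.8's 100 requires 100 randomised. The two sections describe trials that differ in size by a factor of two, and nothing in the documents reconciles them.

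Planned N is the figure that the power statement depends on. A reader who tries to use the stated 80% to work out which N was meant finds that, on the inputs given, it matches neither 25 nor 50 per arm.

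**Working it through.** **Step 1: are the 2.8 totals a slip of multiplication?** Tablets per patient times patients, using 2.8's own schedule:

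| Supply line | As in 2.8 (50 / 50 / 100 patients) | On 2.7's counts (25 / 25 / 50) |
|---|---|---|
| Suvorexant 10 mg | 3×50 + 3×100 = 450 | 3×25 + 3×50 = 225 |
| Suvorexant 20 mg | 4×50 + 87×100 = 8,900 | 4×25 + 87×50 = 4,450 |
| Placebo matching 10 mg | 3×50 = 150 | 3×25 = 75 |
| Placebo matching 20 mg | 4×50 = 200 | 4×25 = 100 |

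Every total in 2.8 reproduces exactly, and its 100 open patients are its own 50 + 50. The doubling lies in the patient counts and runs through all four lines.

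**Step 2: can dropout explain it?** At the 5% expected by week 1, 50/0.95 = 52.6, or 53 patients, not 100. Going from 25 to 50 per arm would need 1 − 25/50 = 50% attrition. Section 2.7 gives no rate for the open phase, but losses there could not raise the counts for the one-week blinded phase.

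**Step 3: the power claim.** Inputs from 2.7: difference 45 min, SD 64, so 45/64 = 0.703, stated as 0.70; two-tailed alpha 0.05; n per arm. For an unadjusted two-sample t test the noncentrality is d·√(n/2) on 2n − 2 degrees of freedom.

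- n = 25: 0.70 × √12.5 = 2.475 on 48 df. Power is 67.9% (68.3% at 0.703; 69.7% by the normal approximation at 0.70). Power of 80% is reached at d = 0.809, which is 0.809 × 64 ≈ 52 min.
- n = 50: 0.70 × √25 = 3.5 on 98 df. Power is 93.4%. Power of 80% is reached at d = 0.566, which is 0.566 × 64 ≈ 36 min.
- 80% power at 0.70 needs 34 per arm (33 by the normal approximation).

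The stated 80% is therefore not reproduced at either N. A one-sided 0.05 test with 25 per arm comes close (78.7% by t, 79.7% by the normal approximation), but 2.7 says two-tailed.

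**Step 4: sensitivity to what 2.7 leaves out.** The outcome is a change, yet 64 is labelled the baseline SD, and neither an SD of change nor a correlation is given. Assume equal SDs at both visits and a baseline-to-Week-1 correlation r from 0.3 to 0.7. This range is an assumption of this review, not a figure in the documents. With 25 per arm:

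- Baseline-adjusted, d = 0.70/√(1 − r²): power 72% to 92%.
- Plain change score, d = 0.70/√(2(1 − r)): power 54% to 88%.

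**Step 5: the supply premise.** Section 2.8 allots three 10 mg tablets and then only 20 mg tablets in each phase. At one tablet a night, a patient who remains at 10 mg is left without 10 mg tablets on that schedule for up to 7 − 3 = 4 blinded nights and 90 − 3 = 87 open nights.

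**The case against.** The strongest reply is that 2.8 is a procurement list. It sets no enrolment target and changes no endpoint, test or analysis set, and 2.7 states its size and its power without ambiguity. Most of this stands. A reader might infer from the mismatch that it is unclear what power the trial claims. The documents do not support that, because 2.7 says 80% on 25 per group and 2.8 makes no power claim. A reader might also infer that the trial really intends 100 patients. That is not shown either, since 2.8 offers no justification for any size. What remains is that 2.8 counts patients by arm, labels none of the stock as spare, and contradicts 2.7.

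On power, a reader might conclude that 80% is unattainable with 25 per arm. That goes too far. The ranges in the fourth step of the working lie on both sides of 80%, so a favourable SD of change could justify the figure. But 2.7 gives no such value, and a correlation picked because it yields 80% would be no justification.

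On supply, a reader might infer that 10 mg stock will run short. The size of this is unknown. If 50 patients are intended and the totals stay as listed, 450 − 225 = 225 active 10 mg tablets are spare. A suvorexant-arm patient who stays at 10 mg throughout needs up to 4 + 87 = 91 more, so the spare stock would cover two such patients. Section 2.3 expects staying at 10 mg in the blinded week to be uncommon, and no count is given.

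**Conclusion.** The inconsistency holds. Section 2.7 plans 50 randomised patients, and 2.8 is built throughout on counts that imply 100: an exact factor of two with no stated overage or dropout allowance. This follows directly from the text of 2.3, 2.7 and 2.8 and needs no assumption.

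The 80% in 2.7 is clearly claimed on 25 per arm but does not follow from the inputs given there: about 68% with 25 per arm, or about 93% with 50. Those two figures assume an unadjusted two-sided t test with 64 used as the SD of the outcome. The planned MMRM could do better or worse, depending on variance inputs that the documents do not supply. The 80% is therefore unsupported as written, rather than shown to be impossible.

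The 10 mg supply premise is a secondary point of unknown size. The documents do not show which N was intended.

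**What to change.** State one planned N and use it in both sections.

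- **If 2.7 governs:** change the patient counts in 2.8 to 25 suvorexant, 25 placebo and 50 open. On 2.8's own per-patient schedule the totals become 225 suvorexant 10 mg, 4,450 suvorexant 20 mg, and 75 and 100 matching placebo tablets. Label any extra stock as overage.
- **If 100 patients were already intended:** change 2.7 to 50 per arm.

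In either case, restate the power in 2.7 for that N on a declared basis (about 68% or about 93% at 0.70, unadjusted), and say whether 64 is the SD of baseline sTST or of its change. Keep 80% for 25 per arm only if 2.7 cites an SD of change or a baseline-to-Week-1 correlation supported by data, not one chosen to reach 80%.

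Before the tablet totals are final, reconcile 2.8's premise that every patient moves to 20 mg on day 4 of each phase with 2.3's allowance to remain at 10 mg.

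The cost is wording and arithmetic in 2.7 and 2.8, and possibly a less favourable stated power. No added enrolment is proposed.
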